13.6.2. Asthma Control Test

Subjects with a medical history of asthma will take an Asthma Control Test (ACT) at Screening, Baseline, Week 4, Week 8, Week 12 and Week 16 of the Initial Period and at Week 20, Week 24, Week 28, Week 32, Week 36, Week 40, Week 44, and Week 48 of the Maintenance Period, as well as at Early termination visit, and Follow-up.

[figure not shown]
The ACT is designed for adults and adolescents 12 years or older, and is composed of 5 questions. For each question, the subject will choose the best answer out of 5 possible answers. The test provides a numerical score ranging from 5 to 25 to assess asthma control; a higher score indicates better asthma control while a score of 19 or less indicates the subject's asthma may not be under control.

Subjects with a new (de novo) diagnosis of asthma during the trial will take the ACT beginning at the visit the diagnosis was first confirmed and at all subsequent study visits thereafter.

ACT total score (absolute values and change from Baseline) will be summarized as a continuous variable (scheduled visits only) for the Initial Treatment Period and the Maintenance Period.

The number and percentage of subjects with an ACT score \leq 19 will be summarized (scheduled visits only) for the Initial Period and the Maintenance Period.

CCI

This document is confidential.

14. Interim Analyses

No interim analysis is planned.

1.0

CD14152.SPR118169.SAP.V01

Approved 10-Nov-2022 00:00:00

This document is confidential.

15. Changes from Analysis Planned in Protocol

In protocol Section 8.4.9 (Prior and Concomitant Therapies), concomitant medications/therapies are defined as any therapies taken during the study (i.e., from the screening visit to the end of study).

However, for the analysis purpose, concomitant medications/therapies are defined as medications/therapies which start or stop or ongoing on or after the 1st injection of study drug.

1.0

CD14152.SPR118169.SAP.V01

Approved 10-Nov-2022 00:00:00

This document is confidential.

16. Reference List

Not applicable.

1.0

CD14152.SPR118169.SAP.V01

Approved 10-Nov-2022 00:00:00

This document is confidential.

17. Programming Considerations

All TFLs and statistical analyses will be generated using SAS® 9.4 or higher (SAS® Institute Inc., Cary, NC, USA). Computer-generated TFL output will adhere to the following specifications.

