#### **9.2.9.1 Asthma Control Test**

Subjects with a medical history of asthma will take the ACT at visits according to Section 8.1.2 before questioning and physical examination by the investigator. Subjects with a new (de novo) diagnosis of asthma will take the ACT beginning at the visit the diagnosis was first confirmed and at all subsequent study visits thereafter. Subjects with an ACT score  $\leq 19$  will be referred to the physician managing their asthma.

The ACT is an assessment to determine if a subject's asthma symptoms are well controlled. The ACT is designed for adults and adolescents 12 years or older, and is composed of 5 questions. For each question, the subject will choose the best answer out of 5 possible answers. The test provides a numerical score ranging from 5 to 25 to assess asthma control; a higher score indicates better asthma control while a score of 19 or less indicates the subject's asthma may not be under control. See [Appendix 12](#).

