13.6. Respiratory Assessments

13.6.1. Respiratory Examination and PEF Testing

A respiratory examination consisting of questions regarding medical history of asthma, wheeze, dyspnea, and cough, will be performed for all subjects at Screening, Baseline, Week 4, Week 8, Week 12 and Week 16 of the Initial Period and at Week 20, Week 24, Week 28, Week 32, Week 36, Week 40, Week 44, and Week 48 of the Maintenance Period, as well as at Early termination visit, and at Follow-up.

Respiratory examination questionnaire results will be listed on the Safety population.

PEF testing will be performed for all subjects at Screening, Baseline, Week 4, Week 8, Week 12 and Week 16 of the Initial Period and at Week 20, Week 24, Week 28, Week 32, Week 36, Week 40, Week 44, and Week 48 of the Maintenance Period, as well as at Early termination visit, and at Follow-up.

This document is confidential.

PEF (absolute values and change from Baseline; and change from Week 16 for the Maintenance Period) will be summarized as a continuous variable (scheduled visits only) for the Initial Period and the Maintenance Period. PEF will be summarized separately for the subset of subjects with, and without, a history of asthma.

The number and percentage of subjects with PEF < 80% will be summarized by treatment group, visit (scheduled visits only), and medical history of asthma (with and without history of asthma) for the Initial Treatment Period and the Maintenance Period.

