17.2.5.2. Table Conventions

- Units will be included where available
- If the categories of a parameter are ordered, then all categories between the maximum and minimum category are presented in the table, even if n=0 for all treatment groups in a given category that is between the minimum and maximum level for that parameter. For example, the frequency distribution for symptom severity would appear as:

Severity Rating	n
severe	0
moderate	8
mild	3

Where percentages are presented in these tables, zero percentages will not be presented and so counts of 0 will be presented as 0 and not as 0 (0%).

This document is confidential.

- If the categories are not ordered (e.g., Medical History, Reasons for Discontinuation from the Study, etc.), then only those categories for which there is at least 1 subject represented are included.
- An Unknown or Missing category are added to each parameter for which information is not available for 1 or more subjects.
- Unless otherwise specified, the estimated mean, median, Q1 and Q3 for a set of values are printed out to 1 more significant digit than the original values, and standard deviations are printed out to 2 more significant digits than the original values. The minimum and maximum should report the same significant digits as the original values. Missing descriptive statistics or p-values which cannot be estimated are reported as “-”.
- Percentage values are printed to one decimal place, in parentheses with no spaces, one space after the count (e.g., 7 (12.8%), 13 (5.4%)). Pre-determine how to display values that round down to 0.0. A common convention is to display as '<0.1', or as appropriate with additional decimal places. Unless otherwise noted, for all percentages, the number of subjects in the analysis population for the treatment group who have an observation will be the denominator. Percentages after zero counts should not be displayed and percentages equating to 100% are presented as 100%, without decimal places.
- Tabular display of data for medical history, prior/concomitant medications, and all tabular displays of adverse event data are presented by the body system, treatment class, or SOC. The body system, drug class and SOC are displayed in alphabetically order. Within body system, drug class and SOC, preferred term will be display in descending frequency. If incidence for more than 1 preferred term is identical, they should then be sorted alphabetically.

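### The ACT tables do not separate subjects with an asthma history from cases diagnosed on study, so the denominator and case mix of their by-visit rows change after randomisation

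*SAP*

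**What the plan says.** **Who takes ACT, and when.** For subjects with a history, SAP 13.6.2 reads "Subjects with a medical history of asthma will take an Asthma Control Test (ACT) at Screening, Baseline, Week 4, Week 8, Week 12", and the visits continue through Week 48 and Follow-up. Protocol 9.2.9.1 gives the rule for new cases: "Subjects with a new (de novo) diagnosis of asthma will take the ACT beginning at the visit the diagnosis was first confirmed". The SAP repeats that rule: "Subjects with a new (de novo) diagnosis of asthma during the trial will take the ACT beginning at the visit the diagnosis was first confirmed".

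**Entry filter.** Protocol 8.3.3, exclusion 2c, removes subjects with ACT of 19 or less at screening or baseline. It applies only to those with an asthma history.

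**Summaries.** SAP 13.6.2 states "ACT total score (absolute values and change from Baseline) will be summarized as a continuous variable", at scheduled visits. It adds "The number and percentage of subjects with an ACT score" of 19 or less. Neither sentence restricts or splits the set, and the table index has one ACT table per period (14.3.4.4.14 and 14.3.4.4.15).

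**Denominator.** The default in SAP 17.2.5.2 is: "for all percentages, the number of subjects in the analysis population for the treatment group who have an observation will be the denominator".

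**Baseline.** SAP 8.2 takes the latest valid value before the first injection. Week 16 serves as Baseline for the Maintenance Period.

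**Contrast with PEF.** SAP 13.6.1 states "PEF will be summarized separately for the subset of subjects with, and without, a history of asthma", and Tables 14.3.4.4.8 to 14.3.4.4.11 carry this out. Protocol 10.1.4.5 also summarises PEF by asthma history.

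**The concern.** New asthma and worsening of known asthma share one AESI category, but they are different signals. Protocol 6.2.3 reports phase 2b flares in subjects with pre-existing asthma in 1.8% on placebo and 12.3% on 30 mg. A natural question for this trial is therefore whether control worsens visit by visit in subjects already known to have asthma.

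A pooled ACT row does not answer that cleanly. A higher share at or below 19 at a later visit, or on one arm, could reflect poorer control in known asthmatics or the arrival of new cases. The change-from-Baseline row cannot settle it, because new cases have no pre-dose value and drop out of it.

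**Working it through.** The documents give no ACT rate, asthma prevalence or rate of new asthma. There is no plan figure to reproduce, so the check is textual first and illustrative second.

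**Step 1: who can contribute to each row**

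| | History at screening | Diagnosed on study |
|---|---|---|
| First ACT | Screening | Diagnosis visit |
| ACT filter at entry | Above 19 required | None |
| Pre-dose Baseline ACT | Yes | No; no imputation rule found |
| Absolute and ACT ≤19 rows | All visits attended | From diagnosis only |
| Change from pre-dose Baseline | Yes | No |

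Pooling is inferred from the missing split and the single table per period; it is not stated. One new case is enough to alter the denominator and leave the change row short of the absolute row. Listing 16.2.8.2.8 (falls of at least 15% from Baseline in PEF or ACT) meets the same gap for ACT.

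The Maintenance table differs in one respect. A case diagnosed in the Initial Period who continues can have a Week 16 ACT. SAP 13.6.2 names only Baseline, whereas SAP 13.6.1 specifies change from both Baseline and Week 16 for PEF.

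**Step 2: illustrative size, Initial Period, nemolizumab arm**

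N = 750 × 2/3 = 500. Everything else is assumed: history in 20% to 40%; new asthma in 1% to 5% of the rest; ACT ≤19 in p = 10% of history subjects and q = 10%, 30% or 60% of new cases.

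H = N × history fraction; D = (N − H) × new-asthma fraction; pooled share = (H·p + D·q)/(H + D).

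| History | New | H | D | D/(H+D) | q = 10% | q = 30% | q = 60% |
|---|---|---|---|---|---|---|---|
| 40% | 1% | 200 | 3 | 1.5% | 10.0% | 10.3% | 10.7% |
| 30% | 3% | 150 | 10.5 | 6.5% | 10.0% | 11.3% | 13.3% |
| 20% | 5% | 100 | 20 | 16.7% | 10.0% | 13.3% | 18.3% |

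The largest value is (100 × 0.10 + 20 × 0.60)/120 = 22/120 = 18.3%. With p = 5% and q = 60%, the first and last rows become 5.8% and 14.2%. All D cases are placed at one visit; because they accrue over time, earlier visits would be affected less.

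**Step 3: comparison of arms**

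Placebo has 250 subjects, so H is 50 to 100 and D is 1.5 to 10. With the same rates, the ratio D/H and hence the pooled share are the same as on nemolizumab. New entrants separate the arms only if the rate of new diagnosis, the prevalence of asthma history or the level of control differs between them.

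**Step 4: Maintenance Period**

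Protocol 8.1 expects about 190 nemolizumab responders re-randomised 1:1:1, so 190/3 ≈ 63 per group. Under the same assumptions the new cases per group run from 63.3 × 0.60 × 0.01 = 0.4 to 63.3 × 0.80 × 0.05 = 2.5. A separate by-visit table for them would be almost empty.

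**The case against.** The strongest reply is that this is ordinary, visible behaviour in a descriptive table. Any change row omits subjects without a baseline value. SAP 8.1 requires n with each continuous summary. SAP 17.2.5.2 sets its denominator only as a default and asks that denominators be explained in footnotes or programming notes. The table shells are not available, so the absence of such a footnote cannot be shown. No test depends on ACT. New cases also appear in the AESI tables, the adjudicated asthma tables and listings, and the ACT listing 16.2.8.2.7. The PEF split serves a different purpose, since PEF is also measured in subjects without asthma.

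Much of this stands, and it limits the weight of the point. Two parts do not remove it. First, none of those summary tables gives ACT control by visit in known asthmatics free of post-randomisation entrants; a reader would have to rebuild that from the listing. Second, the PEF flag does work here. Medical history is collected only at screening (SAP 9.3), so among subjects who take ACT, those without a history are the new cases.

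Two stronger readings are tempting. A reader might infer that the share at or below 19 must drift upward by construction. Only the denominator and case mix change by construction: with q = p the share stays at 10.0%. A reader might also infer that the absolute and change rows describe different subjects. They overlap, because the change rows are a subset of the absolute rows.

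**Conclusion.** The point holds as a minor weakness in a descriptive safety summary of a named risk. SAP 13.6.2 combines a cohort required to have ACT above 19 at entry with subjects who join after randomisation because asthma was diagnosed. That conclusion rests on the text and on reading the unsplit tables as pooled.

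The size cannot be known from the documents. The range of 10.0% to 18.3% against 10% is illustrative and depends on assumed prevalence, incidence and control; with few new diagnoses the effect is small. The documents do not support a claim that the tables will produce a false asthma signal or favour an arm.

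One time trend is unaffected by any split. Exclusion 2c starts eligible history subjects at 0% with ACT ≤19, so their share can only stay at zero or rise above it after Baseline.

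**What to change.** - Base the by-visit ACT score, change from Baseline and ACT ≤19 in Tables 14.3.4.4.14 and 14.3.4.4.15 on subjects with an asthma history at screening, using the flag already used for PEF, with n shown in each row.
- Report new cases separately, by count per arm and a listing from the diagnosis visit, with a summary table only if numbers allow.
- Footnote that change rows cover only subjects with a Baseline ACT, and state whether the Maintenance table uses the pre-dose Baseline, Week 16 or both.

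The cost is a few lines of SAP text and one extra split on data already collected. The drawback is small cells for new cases, especially in maintenance, which is why a count and listing are preferable there to a full by-visit table.

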17.1. General Considerations

- A separate SAS program will be created for each output.
- Each output will be stored in a separate file.
- Output files will be provided in separate Word RTF and PDF format.
- Output files will be delivered in PDF format.
- The final TFLs will be provided in a combined PDF document including a table of contents which are hyperlinked to each output.
- Numbering of TFLs will follow International Conference on Harmonization (ICH) E3 guidance.

17.2. Table, Figure, and Listing Format

17.2.1. General

- All TFLs will be produced in landscape format, unless otherwise specified.
- All TFLs will be produced on paper size A4 using the Courier New font, size 8.
- The data displays for all TFLs will have a 0.8 inch (2cm) binding margin on top and bottom of a landscape oriented page and a minimum 0.3 inch (0.8cm) margin on the left and right sides.
- Headers and footers for figures will be in Courier New font, size 8.
- Legends will be used for all figures with more than 1 variable, group, or item displayed.
- TFLs will be in black and white (no color), unless otherwise specified.
- Specialized text styles, such as bolding, italics, borders, shading, and superscripted and subscripted text, will not be used in the TFLs, unless otherwise specified. On some occasions, superscripts 1, 2, or 3 may be used (see below).
- Only standard keyboard characters will be used in the TFLs. Special characters, such as non-printable control characters, printer-specific, or font-specific characters, will not be used. Hexadecimal-derived characters will be used, where possible, if they are appropriate to help display math symbols (e.g., μ). Certain subscripts and superscripts (e.g., cm², C_{max}) will be employed on a case-by-case basis.
- Mixed case will be used for all titles, footnotes, column headers, and programmer-supplied formats, as appropriate.

17.2.2. Headers

- All output should have the following header at the top left of each page:
 - Galderma Protocol RD.06.SPR.118169
 - Dry-run on dummy treatment/Draft/Final
- All output should have Page n of N at the top corner of each page. TFLs are internally paginated in relation to the total length (i.e., the page number should appear sequentially as page n of N, where N is the total number of pages in the table).
- The date output was generated should appear along with the program name as a footer on each page.

This document is confidential.

17.2.3. Display Titles

- Each TFL are identified by the designation and a numeral. (i.e., Table 14.1.1). ICH E3 numbering is strongly recommended, but sponsor preferences are obtained before final determination. A decimal system (x.y and x.y.z) are used to identify TFLs with related contents. The title is centered. The analysis population are identified on the line immediately following the title. The title and table designation are single spaced. A solid line spanning the margins will separate the display titles from the table.
- Column headers. There will be 1 blank line between the last title and the solid line.

Table x.y.z
 First Line of Title
 Second Line of Title if Needed
 ITT Population

17.2.4. Column Headers

- Column headings are displayed immediately below the solid line described above in Initial upper-case characters.
- In the case of efficacy tables, the variable (or characteristic) column will be on the far left followed by the dose group column.
- For numeric variables, include "unit" in column or row heading when appropriate.
- Analysis population sizes will be presented for dose group in the column heading as (N=XX) (or in the row headings, if applicable). This is distinct from the 'n' used for the descriptive statistics representing the number of subjects in the analysis population.

17.2.5. Body of the Data Display

17.2.5.1. General Conventions

Data in columns of a table or listing are formatted as follows:

- Alphanumeric values are left-justified;
- Whole numbers (e.g., counts) are right-justified; and
- Numbers containing fractional portions are decimal aligned.

17.2.5.2. Table Conventions

- Units will be included where available
- If the categories of a parameter are ordered, then all categories between the maximum and minimum category are presented in the table, even if n=0 for all treatment groups in a given category that is between the minimum and maximum level for that parameter. For example, the frequency distribution for symptom severity would appear as:

Severity Rating	n
severe	0
moderate	8
mild	3

Where percentages are presented in these tables, zero percentages will not be presented and so counts of 0 will be presented as 0 and not as 0 (0%).

This document is confidential.

- If the categories are not ordered (e.g., Medical History, Reasons for Discontinuation from the Study, etc.), then only those categories for which there is at least 1 subject represented are included.
- An Unknown or Missing category are added to each parameter for which information is not available for 1 or more subjects.
- Unless otherwise specified, the estimated mean, median, Q1 and Q3 for a set of values are printed out to 1 more significant digit than the original values, and standard deviations are printed out to 2 more significant digits than the original values. The minimum and maximum should report the same significant digits as the original values. Missing descriptive statistics or p-values which cannot be estimated are reported as “-”.
- Percentage values are printed to one decimal place, in parentheses with no spaces, one space after the count (e.g., 7 (12.8%), 13 (5.4%)). Pre-determine how to display values that round down to 0.0. A common convention is to display as '<0.1', or as appropriate with additional decimal places. Unless otherwise noted, for all percentages, the number of subjects in the analysis population for the treatment group who have an observation will be the denominator. Percentages after zero counts should not be displayed and percentages equating to 100% are presented as 100%, without decimal places.
- Tabular display of data for medical history, prior/concomitant medications, and all tabular displays of adverse event data are presented by the body system, treatment class, or SOC. The body system, drug class and SOC are displayed in alphabetically order. Within body system, drug class and SOC, preferred term will be display in descending frequency. If incidence for more than 1 preferred term is identical, they should then be sorted alphabetically.
 - P-values are presented with 4 decimal places. If the p-value is less than 0.0001, it will be presented as <0.0001. If the p-value is returned as >0.9999, it is presented as >0.9999.
 - The percentage of subjects is normally calculated as a proportion of the number of subjects assessed in the relevant treatment group (or overall) for the analysis population presented. However, careful consideration is required in many instances due to the complicated nature of selecting the denominator, usually the appropriate number of subjects exposed. Describe details of this in footnotes or programming notes.
 - For categorical summaries (number and percentage of subjects) where a subject can be included in more than one category, describe in a footnote or programming note as needed if the subject are included in the summary statistics for all relevant categories or just 1 category and the criteria for selecting the criteria.
 - Where a category with a subheading (such as system organ class) has to be split over more than one page, output the subheading followed by “(cont)” at the top of each subsequent page. The overall summary statistics for the subheading should only be output on the first relevant page.

17.2.5.3. Listing Conventions

- Listings will be sorted for presentation in order of subject number, visit/collection day, and visit/collection time.
- Missing data are represented on subject listings as either a hyphen (“-”) with a corresponding footnote (“- = unknown or not evaluated”), or as “N/A”, with the footnote “N/A = not applicable”, whichever is appropriate.
- Dates are printed in SAS DATE9.format (“DDMMYYYY”: 01JUL2000). Missing portions of dates are represented on subject listings as dashes (--JUL2000). Dates that are missing because they are not applicable for the subject are output as “N/A”, unless otherwise specified.

This document is confidential.

- All observed time values are to be presented using a 24-hour clock HH:MM or HH:MM:SS format (e.g., 11:26:45, or 11:26). Time will only be reported if it was measured as part of the study.
- Units will be included where available.

17.2.5.4. *Figure Conventions*

- Unless otherwise specified, for all figures, study visits will be displayed on the X-axis and endpoint (e.g., treatment mean change from Baseline) values will be displayed on the Y-axis.

